AE	Adverse Event
CAC	Central Adjudication Committee
CRF	Case Report Form
DSMC	Data Safety and Monitoring Committee
EDC	Electronic Data Capture
FAITH	Fixation using Alternative Implants for the Treatment of Hip Fractures
HOS	Hip Outcome Score
HRQL	Health-Related Quality of Life
IU	International Units
MRI	Magnetic Resonance Imaging
nmol/L	Nanomole/Litre
PHI	Personal Health Information
RCT	Randomized Controlled Trial
REB	Research Ethics Board
RRR	Relative Risk Reduction
SAE	Serious Adverse Event
SF-12	Short Form-12
SHS	Sliding Hip Screw

STUDY SUMMARY

Title	Fixation using A lternative I mplants for the T reatment of H ip Fractures (FAITH-2): A Multi-Centre 2x2 Factorial Randomized Trial Comparing Sliding Hip Screws versus Cancellous Screws AND Vitamin D versus Placebo on Patient Important Outcomes and Quality of Life in the Treatment of Young Adult (18-60) Femoral Neck Fractures
Short Title	FAITH-2
Methodology	Concealed 2x2 factorial randomized controlled trial
Clinical Sites	Multiple international clinical sites
Primary Objective	The primary objective is to assess the impact of surgical implant (sliding hip screws versus cancellous screw fixation) AND nutritional supplementation (vitamin D versus placebo) on a composite of patient important outcomes during the 12 month post-surgery follow-up period. The composite of patient important outcomes includes: re-operation, femoral head osteonecrosis, severe femoral neck malunion, and nonunion.
Secondary Objectives	To assess the impact of surgical implant (sliding hip screw fixation versus cancellous screw fixation) and nutritional supplementation (vitamin D versus placebo) on health-related quality of life and functional outcomes, fracture healing complications, and radiographic fracture healing.
Sample Size	We will recruit a sample size of 808 patients with full follow-up. Based on an anticipated 10% loss to follow-up, 898 patients will need to be enrolled in the FAITH-2 trial.
Diagnosis and Main Inclusion Criteria	Femoral neck fracture in patients between the ages of 18 and 60.
Study Products	Surgical implants: Sliding hip screw versus multiple cancellous screws. Nutritional supplementation: Vitamin D ₃ (4,000 International Units/day taken for 6 months) versus placebo taken for 6 months.
Length of Follow-Up	12 months.

1. INTRODUCTION

This document is a protocol for a human research study that seeks to identify a surgical and nutritional strategy to minimize fracture fixation complications and optimize bone health in order to improve patient outcomes following a femoral neck fracture. Using a concealed 2x2 factorial design, this multi-centre randomized controlled trial (RCT) compares two alternative surgical implants (cancellous screws and sliding hip screws (SHS)) AND vitamin D supplementation versus placebo for the treatment of femoral neck fractures in young adult patients (aged 18-60). This trial is registered at clinicaltrials.gov (Identifier number: NCT01908751).

1.1 Femoral Neck Fracture in Young Patients

Globally, hip fractures rank in the top 10 of all cause disability adjusted life years lost.¹ Hip fractures predominately affect elderly people, however, it is estimated that over 300,000 hip fractures occur worldwide in patients under the age of 50 annually.^{2,3} Unlike other hip fractures, femoral neck fractures are usually associated with a critical vascular injury that impedes local fracture healing and obliterates the blood supply to the femoral head.⁴ This occurs because the important blood vessels of the proximal femur are small, fragile, and most vulnerable to injury at the femoral neck (**Figure 1**). Ultimately, this vascular injury is the primary cause of two devastating complications: femoral neck nonunion (the fracture does not heal) and femoral head osteonecrosis (bone death). These fractures in younger aged patients are associated with high complication rates and profound impairments in quality of life and function.

Virtually all patients with a femoral neck fracture require surgical management of their injury. Surgical options include arthroplasty (joint replacement) or internal fixation. Arthroplasty is often a successful treatment for elderly patients because it removes the fractured area, obviating the risk of fracture healing complications. However, the primary limitation of arthroplasty is the finite lifespan of the implant. Consequently, arthroplasty is not usually considered an optimal treatment option for younger patients. In addition, younger patients have higher functional demands for work and recreational activities that are not well tolerated by joint replacements. For example, Swedish Hip Registry data shows that younger patients experience higher failure rates than elderly patients (9-year survival rates 87.6% for patients aged 55 years of age or younger compared to 97.0% for patients aged 75 years and older) demonstrating that a revision joint replacement is frequently required.⁵ In addition, revision hip arthroplasty results in worse functional outcomes than primary joint replacements, represent increased morbidity, and may prevent young patients from returning to their pre-injury function.⁶ As result, internal fixation is frequently used to manage the majority of femoral neck fractures in younger patients.

1.2 Internal Fixation of Femoral Neck Fractures

Internal fixation is performed for nearly all femoral neck fractures in young patients to allow patient ambulation, promote healing, and preserve the native hip joint. Young adult femoral neck fractures are typically the result of road traffic accidents and other

high-energy traumas. As a result of their high-energy mechanisms, 80% of these fractures are severely displaced; a state in which the fracture ends are widely separated from each other.⁷ During internal fixation surgery, the fracture ends are put together and a metal implant is inserted into the bone to secure the fracture. Unfortunately, complications following internal fixation are common and include femoral head osteonecrosis, early implant failure, and nonunion of the fracture. A previous meta-analysis that included 18 studies of patients between 15 and 50 years of age with acute intracapsular hip fractures has reported that these major fracture healing complications occur in approximately 25% of patients.⁷ Invariably, these patients endure prolonged morbidity and require further surgery, as confirmed by a 20% re-operation rate in a recent meta-analysis performed by our group.⁸ Beyond the prolonged morbidity and increased healthcare costs associated with re-operations, even patients who do not suffer a fracture healing complication frequently experience poor outcomes. This occurs because an additional 30% of femoral neck fractures heal in a shortened or non-anatomic position.⁹ This alters the mechanics of the hip, causes the leg to be shorter, and results in substantially worse functional outcomes and quality of life. Therefore, the young femoral neck fracture population is at great risk for experiencing significant fracture healing complications, re-operations, and lifelong morbidity.

1.3 Methods of Internal Fixation

The most common methods of internal fixation for the management of femoral neck fractures are multiple cancellous screws or a single compression screw and sideplate (SHS). Both approaches have strong physiologic rationale; however, there is no clinical consensus regarding the optimal approach for managing femoral neck fractures in young adults.¹⁰

1.3.1 Multiple Cancellous Screws

Cancellous screws have traditionally been the preferred internal fixation implant for femoral neck fractures.¹¹ Multiple screws (2 or more) are used during fixation, and advocates of this implant promote the construct's superior torsional stability, limited disruption of femoral head blood supply, minimally invasive insertion, and retention of more viable bone than the SHS.^{12,13,14,15,16} Retaining more cancellous bone optimizes vascularity and thus may reduce the risk of femoral head osteonecrosis. In addition, surgeons can insert cancellous screws using small stab incisions with limited blood loss and operating time. This minimally invasive approach may limit damage to the soft tissues around the hip and may plausibly lead to better patient function. The use of cancellous screws has also been supported by two small RCTs. One study compared three cancellous screws versus the larger SHS in patients of all ages and found 3.5-fold greater femoral head vascularity at follow-up bone scanning in patients treated with cancellous screws.¹⁵ The other small RCT compared cancellous screws and SHSs in 30 young adult patients. This study suggested that the use of cancellous screws led to decreased operative time (80% of cases were less than one hour in the cancellous screw group vs. 67% in the SHS group), superior functional outcomes (60% of cases were rated as excellent using the Judet classification system versus 33% in the SHS group), and

fewer complications (2 complications in the cancellous screws group vs. 9 in the SHS group).¹⁷ The small sample size of this study limits our ability to draw definitive conclusions regarding the optimal method of internal fixation.

1.3.2 Sliding Hip Screws

Although cancellous screw fixation has many theoretical benefits and two small RCTs provide evidence supporting its use versus SHS, previous research has suggested that cancellous screws typically fail from bending or shear forces. Since a more vertical high-energy fracture is frequently seen in young adults, proponents of the SHS believe that the implant's biomechanical properties and greater fracture stability are important factors to counteract these forces.¹⁸ Biomechanical studies have shown SHS constructs have 2-fold greater maximal strength and less displacement under physiologic loading conditions compared to cancellous screws.¹⁹ The SHS also performed better than cancellous screws in stabilizing unstable femoral neck fractures using cyclic loading models.^{20,14} In addition, two recent retrospective studies comparing cancellous screws and the SHS in young adult fractures have shown substantial reductions in short-term complications using the SHS. Gardner et al²¹ showed a 18% absolute risk reduction for re-operation at 6 months (6/29 (21%) patients in the cancellous screw group versus 1/40 (3%) patients in the SHS group). Chen et al²² reported a 25% absolute risk reduction for reoperation at an average of 15 months (7/28 (25%) patients in the cancellous screw group versus 0/23 (0%) of patients in the SHS group). Other more heterogeneous retrospective studies by Liporace et al²³ and Razik et al²⁴ suggest Relative Risk Reductions (RRRs) from SHS between 50% to 88% for osteonecrosis of the femoral head and 63% for nonunion. While conclusions from these studies are limited by small sample sizes and the fact that the data are not adjusted for risk, these large reported treatment effects favouring the SHS suggest that a substantial reduction in complications may be achieved by using this alternative surgical implant.

1.3.3 Inconclusive Clinical Evidence

We have conducted two systematic reviews to characterize the outcomes of femoral neck fractures in young patients treated with internal fixation and have performed comprehensive reviews of other relevant literature.⁸ These reviews and a meta-analysis by Damany et al⁷ document a 25% incidence of fracture complications, a 20% re-operation rate, and a 30% fracture malunion incidence associated with poor quality of life. Our reviews also revealed conflicting data from a small number of studies comparing the SHS and cancellous screws; however, these studies were too heterogeneous to facilitate any quantitative pooling of the results to compare cancellous screw and SHS fixation.

The impact of uncertainty in the surgical literature is further demonstrated by a lack of surgeon consensus. We recently conducted an international survey of orthopaedic surgeons to determine their treatment preferences for the management of young femoral neck fractures.¹⁰ The survey was completed by 540 orthopaedic surgeons. For displaced fractures, 49% of respondents prefer the SHS and 46% prefer cancellous screw

fixation. Despite a near equal split in preference between the SHS and cannulated screws, most surgeons indicated they had treated at least one femoral neck fracture with each device in the past 12 months. The majority of respondents endorsed the need for a RCT comparing SHS and cannulated screws (268/476, 56.3%).

1.4 Adjuvant Nutritional Supplementation (Vitamin D)

Vitamin D is a nutrient that helps the body use calcium and phosphorous to build and maintain strong bones.²⁵ Vitamin D plays an important role in musculoskeletal health and bone quality because it regulates serum calcium homeostasis. Too little vitamin D can cause calcium and phosphorus levels in the blood to decrease, leading to calcium shifting out of the bones to help maintain stable blood levels.²⁵

Laboratory research and human clinical studies suggest important associations between vitamin D, musculoskeletal health, and improved fracture healing. Experimental animal studies have demonstrated the concentration of vitamin D metabolites are higher at a fracture callus compared to the uninjured contralateral bone,²⁶ vitamin D supplementation leads to decreased time to fracture union and increased callus vascularity,²⁷ and vitamin D increases mechanical bone strength compared to controls.²⁸ Clinical studies have also demonstrated that vitamin D supplementation increases the callus volume of proximal humerus fractures,²⁹ increases the number and diameter of type II muscle fibres,² and can improve wound healing.³⁰ It also has preventative bone health benefits in young adult populations. For example, in a double-blind, placebo-controlled RCT examining the impact of vitamin D on stress fractures in 3,700 navy recruits, a 20% RRR was observed for developing a stress fracture (6.8% experienced a stress fracture in the vitamin D group versus 8.6% in the placebo group).³¹ These findings highlight the importance of vitamin D in musculoskeletal health.

By helping to maintain bone health and prevent vitamin D deficiency, the potential benefits of vitamin D supplementation are even more relevant in light of recent research demonstrating that as many as 8 of 10 trauma patients are vitamin D insufficient.^{32,33,34} In 201 patients admitted to a level 2 trauma centre for fracture surgery, Bee et al reported the highest prevalence of vitamin D insufficiency was in patients ages 21-40 years (80.5%).³² Additionally, in a sample of 1,830 fracture patients from a level 1 trauma centre Crist et al reported that 77.4% had vitamin D insufficiency.^{33,34} Similar age related results were also found: 79.4% in patients ages 26-35, 81.3% of patients ages 36-45, and 81.6% in patients ages 56-65.³⁴ The high prevalence of vitamin D insufficiency among young trauma patients combined with the critical microvascular injury at the femoral neck site suggests these fracture patients may face significant barriers to healing and achieving good functional outcomes.

Although the biologic rationale to use vitamin D supplementation to nutritionally optimize the bone of health of young fracture patients is compelling, more clinical research is needed.³⁵ In this clinical trial, an oral daily dose of 4,000 International Units (IU) of vitamin D₃ has been selected as the route and dose for vitamin D

supplementation. According to a 2010 U.S. Institute of Medicine report jointly commissioned by the U.S. and Canadian governments, 4,000 IU is the Tolerable Upper Intake Level of vitamin D per day for individuals' aged 9 years or older.³⁶ The rationale for using this dose in the current clinical trial is centred upon our goals of quickly reversing any potential vitamin D insufficiency in a safe and patient-friendly manner. This dose can readily be achieved orally with self-administered pills or drops, and meets the Health Canada criteria for appropriate self-care use.³⁶ A vast range of other oral dosing regimens have been successfully used in other clinical trials. These include a single administration "megadose" (up to 500,000 IU vitamin D₃ given once), a "megadose" followed by large monthly doses (500,000 IU vitamin D₃ once and monthly 50,000 IU vitamin D₃), and even smaller daily doses alone (1,000 IU vitamin).^{37,38} A RCT of hip fracture patients over age 50 demonstrated that there is no advantage of a loading dose in addition to daily supplementation with 1,000 IU vitamin D₃.³⁸ At 3 months, there was no difference in the serum vitamin D levels between the treatment groups and a similar proportions of patients in each group reached the goal of >75 Nanomole/Litre (nmol/L).³⁸ Therefore, the daily dose of 4,000 IU of vitamin D₃ should be sufficient to reverse any nutritional insufficiency during the critical first few months of fracture healing.

2. STUDY OBJECTIVES

The objectives of this study are to determine the impact of surgical implants (SHS versus cancellous screw fixation) *AND* nutritional supplementation (vitamin D supplementation versus placebo) on young adults (aged 18-60) with femoral neck fractures. This will be assessed through the following objectives.

2.1 Primary Objective

The primary objective is to assess the impact of surgical implant (SHS versus cancellous screw fixation) *AND* nutritional supplementation (vitamin D versus placebo) on a composite of patient important outcomes during the 12 month post-surgery follow-up period. The composite of patient important outcomes includes: re-operation, femoral head osteonecrosis, severe femoral neck malunion, and nonunion.

2.2 Secondary Objectives

Secondary objectives are to assess the impact of the surgical implants and nutritional supplementation on:

1. Health-related quality of life (HRQL) and functional outcomes
2. Fracture healing complications
3. Radiographic fracture healing

3. TRIAL DESIGN

FAITH-2 is a multi-centre, concealed 2x2 factorial RCT. Surgeons will use one of two surgical strategies in patients who have sustained a femoral neck fracture. The first strategy involves fixation using multiple cancellous screws (cancellous screw group). The second treatment strategy involves fixation of the fracture with a large single diameter

screw and side plate (SHS group). Furthermore, participants will be randomized to receive a nutritional supplement (vitamin D supplementation versus placebo). Our recruitment target is 808 patients with full follow-up. Based on an anticipated conservative 10% loss to follow-up³⁹, 898 patients will need to be enrolled in the FAITH-2 trial to meet our target sample size. Study personnel at the clinical sites will document critical aspects of peri-operative care and rehabilitation. Clinical assessments will occur at the time of enrollment (baseline), surgery, post-surgery, and 6 weeks, 3 months, 6 months, 9 months, and 12 months post-surgery.

4. METHODS

4.1 Study Setting

The FAITH-2 trial will be conducted at academic and community hospitals across North America, Europe, Australia, Asia, and South America that treat femoral neck fractures in young adults.

4.2 Eligibility Criteria

Wide eligibility criteria will be used to increase the generalizability of the trial.

4.2.1 Inclusion Criteria

1. Adult men or women ages 18 to 60 years.
2. Fracture of the femoral neck.
3. Fracture amenable to both surgical treatments (SHS and cancellous screws).
4. Operative treatment within 7 days of injury.
5. Provision of informed consent by patient or substitute decision maker.

4.2.2 Exclusion Criteria

1. Patients with previously diagnosed osteoporosis.
2. Fracture-dislocation of the femoral neck and hip joint.
3. Planned antegrade nailing of an ipsilateral femoral shaft fracture (if present).
4. Current infection around the hip (i.e. soft tissue or bone).
5. Stress fracture of the femoral neck.
6. Pathologic fractures secondary to neoplasm or other bone lesion.
7. Patients with known or likely undiagnosed disorders of bone metabolism such as Paget's disease, osteomalacia, osteopetrosis, osteogenesis imperfect, etc.
8. Patients with hyperhomocysteinemia.
9. Patient has an allergy to vitamin D or another contraindication to being prescribed vitamin D.
10. Patient is currently taking an over counter drug and/or food supplement that contains vitamin D and is unable or unwilling to discontinue its use for this study.
11. Likely problems, in the judgment of the attending surgeon, with maintaining follow up (e.g. patients with no fixed address, plans to move out of town).

This may include patients with severe mental disorders and drug addictions without adequate support.

12. Pregnancy.
13. Patient is incarcerated.
14. Patient is not expected to survive injuries.
15. The attending surgeon believes the patient should be excluded because they are involved in a conflicting clinical trial.

We will include all femoral neck fracture patterns (subcapital, midcervical, or basicervical). Ipsilateral femoral shaft fractures treated with retrograde nailing or plating will be eligible for inclusion. Patients with multiple traumas will also be eligible for inclusion. Patients with bilateral femoral neck fractures will be eligible for inclusion; however, only the most severe eligible fracture will be included (defined as the most displaced fracture, as determined by the attending surgeon).

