5.2.3 Secondary Analyses

All secondary outcomes will be summarized using means and 95% confidence intervals, or percentages and 95% confidence intervals. Longitudinal models will be used to explore the effect of treatment group and time on the HOS and SF-12 patient-reported outcomes. **Table 4** shows the details for the analysis of secondary outcomes.

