		Relative Risk Reduction from the SHS and vitamin D supplementation					
		20%	25%	30%	33%	35%	40%
Incidence of Patient Important Outcomes in the control groups	20%	2994	1890	1294	1060	936	706
	25%	2266	1434	984	808	714	540
	30%	1782	1130	778	638	566	428
	35%	1436	914	630	518	460	348
	40%	1178	752	520	428	380	288

- Total sample size required to achieve 80% power for the independent comparisons of the SHS versus cancellous screws AND vitamin D supplementation versus placebo.
- Grey highlighted boxes denote scenarios where we have more than 80% power (alpha=0.05, 2-sided) to detect the hypothesized difference, given our proposed sample size of 808.
- Control groups: cancellous screws and placebo supplementation

Table 3: Summary of Primary Outcome Analyses

Variable/Outcome	Hypothesis for Surgical Treatments	Hypothesis for Nutritional Supplementation	Outcome Measures	Method of Analysis
Re-operation	The incidence of re-operation, femoral head osteonecrosis, severe femoral neck malunion, or nonunion will be lower in patients receiving a SHS compared to cancellous screws.	The incidence of re-operation, femoral head osteonecrosis, severe femoral neck malunion, or nonunion will be lower in patients receiving vitamin D versus placebo.	Re-operation anytime within 12 months	Chi-square statistic with independent comparison for the surgical treatments and nutritional treatments (alpha=0.05)
Femoral head osteonecrosis			Evidence of femoral head osteonecrosis on X-Rays or MRI	
Severe malunion			Evidence of severe femoral neck malunion on X-Rays	
Nonunion			Failure of the fracture to progress towards healing defined as a Radiographic Union Score for Hip (RUSH) ^{41,42} score below a pre-determined threshold specific for nonunion at 6 months or greater post-injury	

[figure not shown]
*The primary outcome is a composite of re-operation, femoral head osteonecrosis, severe femoral neck malunion, or nonunion.

Table 4: Summary of Secondary Analyses

Variable/Outcome	Hypothesis for Surgical Treatments	Hypothesis for Nutritional Supplementation	Outcome Measures	Method of Analysis
HRQL and function	HRQL and function will be better in patients receiving SHS versus cancellous screws.	HRQL and function will be better in patients receiving vitamin D versus placebo.	HOS and SF-12	Summary statistics of means and confidence interval Longitudinal modeling to include treatment and time

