5.0 INJURY AND FRACTURE CHARACTERISTICS

Injury details and fracture characteristics will be summarized in **Table 3**. Pre-operative and post-operative care details (**Table 4**) will be presented for each surgical treatment and nutritional supplementation group. Means and SDs will be used for continuous data, and categorical data will be presented as frequencies and proportions.

Table 3: Fracture Characteristics

Characteristic	Variable	Surgical Treatment X N=	Surgical Treatment Y N=	Nutritional Supplementation X N=	Nutritional Supplementation Y N=	Total N=
Level of the Fracture Line, n (%) Subcapital Midcervical Basal Unable to assess	Adjudicated Data					
Garden Classification, n (%) Garden I (undisplaced) Garden II (undisplaced) Garden III (displaced) Garden IV (displaced) Unable to assess	Adjudicated Data					
Pauwels' Classification, n (%) Type I Type II Type III Unable to assess	Adjudicated Data					
Mechanism of Injury, n (%) Motor Vehicle Accident (Driver/Passenger) Motor Vehicle Accident (Pedestrian) Motorcycle Accident Recreational Vehicle (4 Wheeler, Snowmobile, ATV, etc) Bicycle Accident Fall from Height (>1m) Fall from Height (≤1m) Fall from Standing Direct Trauma (Blunt) Direct Trauma (Penetrating)	3.3 Q15					
Additional Fractures, n (%) Upper extremity Lower extremity Spine and sacrum Pelvis	3.4 Q20					
Additional Injuries, n (%) Chest Injury Abdominal Injury Head/Neck Injury Soft Tissue Injuries to Extremities	3.4 Q24					

Characteristic	Variable	Surgical Treatment X N=	Surgical Treatment Y N=	Nutritional Supplementation X N=	Nutritional Supplementation Y N=	Total N=
Ipsilateral Femoral Shaft Fracture, n (%)	3.5 Q23					

Table 4: Summary of Pre-Operative and Post-Operative Care Details

Characteristic	Variable	Surgical Treatment X N=	Surgical Treatment Y N=	Nutritional Supplementation X N=	Nutritional Supplementation Y N=	Total N=
Pre-operative Antibiotic Prophylaxis, n (%)	3.5 Q26					
Discharge Location, n (%) Home Rehabilitation Facility Other Hospital Medical Respite	7.1 Q2					
Provided with Nutritional Supplement, n (%)	7.1 Q3					
Received Nutritional Supplement Within Two Weeks of Femoral Neck Surgery, n (%)	7.1 Q5					
Nutritional Instructions and Importance of Complying with Nutritional Supplementation Discussed with Participant, n (%)	7.1 Q6					

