9.1 SF-12 Health Survey

The SF-12 Health Survey is a standardized instrument to measure health-related quality of life. This self-administered, 12-item questionnaire covers eight main health domains that make up the Physical and Mental Health Composite Scores (PCS & MCS). Each domain consists of one or two questions and is scored separately from 0 (lowest level) to 100 (highest level).⁴ The SF-12 will be summarized using means and 95% CIs at 10-week, 3, 6, 9, and 12-month intervals (**Tables 13, 14, and 15**). Longitudinal models will be used to explore the effect of treatment group and time on the SF-12 patient-reported outcomes (**Figures 4-9**).

Table 13: HRQL (SF-12), According to Surgical Treatment (No Significant Interaction Between Implant Type and Supplementation Present)

Endpoint	Surgical Treatment X		Surgical Treatment Y		Total	
	N=	Mean (SD)	N=	Mean (SD)	N=	Adjusted Mean Difference (95% CI)
Physical Composite Scale (PCS) Scores						
Post-op						
10 weeks						
3 months						
6 months						
9 months						
12 months						
Mental Health Composite Scale (MCS) Scores						
Post-op						
10 weeks						
3 months						
6 months						
9 months						
12 months						

Table 14: HRQL (SF-12), According to Nutritional Supplementation (No Significant Interaction Between Implant Type and Supplementation Present)

Endpoint	Nutritional Supplementation Treatment X		Nutritional Supplementation Treatment Y		Total	
	N=	Mean (SD)	N=	Mean (SD)	N=	Adjusted Mean Difference (95% CI)
Physical Composite Scale (PCS) Scores						
Post-op						
10 weeks						
3 months						
6 months						
9 months						
12 months						
Mental Health Composite Scale (MCS) Scores						
Post-op						
10 weeks						
3 months						
6 months						
9 months						
12 months						

Figure 4: SF-12 PCS Scores Over Time by Surgical Treatment Group (No Significant Interaction Between Implant Type and Supplementation Present)

[figure not shown]

Figure 5: SF-12 MCS Scores Over Time by Surgical Treatment Group (No Significant Interaction Between Implant Type and Supplementation Present)

[figure not shown]

Figure 6: SF-12 PCS Scores Over Time by Nutritional Supplementation Group (No Significant Interaction Between Implant Type and Supplementation Present)

[figure not shown]

Figure 7: SF-12 MCS Scores Over Time by Nutritional Supplementation Group (No Significant Interaction Between Implant Type and Supplementation Present)

[figure not shown]

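### The SF-12 and HOS models name only treatment and time, yet the SAP tables promise an adjusted difference with no covariates listed, and recorded associated injuries go unused

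*Combined protocol and SAP*

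**What the plan says.** **Who is enrolled.** The text after the exclusion list in protocol 4.2.2 says "Patients with multiple traumas will also be eligible for inclusion". It also says "Patients with bilateral femoral neck fractures will be eligible for inclusion; however, only the most severe eligible fracture will be included". Protocol 1.2 attributes these fractures mainly to high-energy trauma, so associated injuries are to be expected.

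**What is recorded.** SAP Table 3 has the rows "Additional Fractures, n (%) Upper extremity Lower extremity Spine and sacrum Pelvis" (3.4 Q20) and "Additional Injuries, n (%) Chest Injury Abdominal Injury Head/Neck Injury Soft Tissue Injuries to Extremities" (3.4 Q24). Both are summarised as counts and percentages and appear in no model.

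**What is modelled.** Protocol 5.2.3: "Longitudinal models will be used to explore the effect of treatment group and time on the HOS and SF-12 patient-reported outcomes". Protocol Table 4: "Longitudinal modeling to include treatment and time". SAP 9.1: "Longitudinal models will be used to explore the effect of treatment group and time on the SF-12 patient-reported outcomes". SAP 9.2 says the same for the HOS. None of these names a covariate, a baseline score or a stratification factor.

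**What is reported.** SAP Tables 13 to 18 each have an *Adjusted Mean Difference* column with a 95% CI. No section says what the adjustment is.

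**What is balanced by design.** Protocol 4.4 stratifies on displacement, ipsilateral femoral shaft fracture and region type. Other injuries and a contralateral hip fracture are not strata.

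**The concern.** There are two linked gaps. First, the text describes a model of treatment and time while the tables promise an adjusted estimate. Two analysts could report different numbers from the same data, and the choice could be made after the results are visible. Second, an injury to the pelvis, spine, another limb or the head can lower a self-reported health or function score whatever implant or supplement was given. Such injuries are likely to predict the outcome and are already on file. Leaving them out of the model puts that variation into the error term.

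Health-related quality of life is in the trial title, and with function it is the first secondary objective. What is at stake is the width of those confidence intervals and the reproducibility of the reported estimate.

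**Working it through.** **1. The plan's own figure.** The documents give no SD, target difference or power for SF-12 or HOS. The only sample-size figure is for the primary composite: 25% versus 25% × 0.67 = 16.75%, two-sided alpha 0.05, 80% power. The continuity-corrected two-proportion formula gives 404 per arm, or 808 in total (760 without the correction). Then 808/0.9 = 897.8, or 898 enrolled. Both figures reproduce, and neither depends on this point.

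**2. Are the injury items baseline data?** This is inferred. Form 3 also holds the row beginning "Pre-operative Antibiotic Prophylaxis, n" (3.5 Q26), form 4 holds the operation, and protocol Table 1 places the Pre-Operative Form at enrolment. Together these put 3.4 Q20 and Q24 before surgery.

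**3. Would a baseline score do the same job?** No. Under protocol 4.9 and the footnote to protocol Table 1, the first SF-12 and HOS ask about status before the injury. That score cannot carry the burden of the new injuries.

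**4. Precision.** Let p be the share of participants with another injury and d their score deficit, in SDs among participants alike on injury. Neither is in the documents; I assume p = 0.20 to 0.50 and d = 0.3 to 0.8. For one indicator and a comparison at one visit:

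- R² = p(1−p)d² / [1 + p(1−p)d²]
- SE reduction = 1 − √(1−R²)
- equivalent unadjusted N = 808/(1−R²)

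| p | d | R² | SE reduction | 80% power becomes | Equivalent N |
|---|---|---|---|---|---|
| 0.20 | 0.3 | 0.0144/1.0144 = 0.014 | 0.7% | 80.6% | 820 |
| 0.35 | 0.5 | 0.0569/1.0569 = 0.054 | 2.7% | 82.1% | 854 |
| 0.50 | 0.8 | 0.1600/1.1600 = 0.138 | 7.2% | 85.5% | 937 |

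**5. Chance imbalance.** With m per arm, the 95% range of imbalance is 1.96√[2p(1−p)/m], and the resulting shift is d times that.

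- N = 808 (m = 404): ±5.5 to 6.9 percentage points, a shift of at most 0.017 to 0.055 SD. The difference detectable with 80% power is 2.80 × √(2/404) = 0.197 SD.
- N = 86 (m = 43, as printed in SAP Table 2): ±16.9 to 21.1 points, a shift of at most 0.051 to 0.169 SD. The detectable difference is 2.80 × √(2/43) = 0.604 SD.

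The shift is in residual SDs and the detectable difference in total SDs. The two scales differ by at most a factor of √1.16 = 1.08.

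**6. Is imbalance a second harm?** Take p = 0.3, d = 0.8, m = 404. The variance due to imbalance is 2(0.21 × 0.64)/404 = 2(0.1344)/404. The total variance of the unadjusted difference is 2(1.1344)/404. The ratio is 0.1344/1.1344 = 0.118, which is R² itself. The possible shift of about 0.05 SD already lies inside the unadjusted 95% half-width of 1.96√[2(1.1344)/404] = 0.147 SD. Imbalance and the wider interval are one loss.

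**The case against.** The case for leaving the plan alone is that these are secondary models meant to explore effects, the trial was not sized for them, and randomisation keeps the unadjusted difference unbiased with correct coverage. The gain is small and rests on assumed inputs. All of that stands, and it limits the point to modest precision. It does not answer the undefined adjusted column.

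Several stronger readings are tempting, and the documents do not support them:

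- *The models contain nothing but treatment and time.* Those are the only terms named. Protocol Table 4 says the modelling is to include them, SAP 8.0 carries a significant implant-by-supplement interaction into later analyses, and the tables promise some adjustment.
- *Randomisation ignores associated injury.* It stratifies on ipsilateral shaft fracture. Only the remaining injuries are left to chance.
- *Imbalance could create a false treatment effect.* Not beyond the nominal error rate; step 6 shows that it is already in the interval.
- *A contralateral femoral neck fracture is captured by Q20.* The SAP Table 3 row lists only body regions, and bilateral fracture has no row of its own.
- *The HOS is a whole-person measure.* Protocol 4.8.2 describes a hip score covering daily activities and sport. How far a chest or arm injury lowers it is unknown, which is why the assumed range starts at 0.3 SD.

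Adjusting for injuries alone would also be hard to defend, because the stratification factors and the pre-injury score have at least as strong a claim.

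**Conclusion.** The point holds as a specification gap with a modest efficiency cost. The plan promises adjusted SF-12 and HOS differences without defining the adjustment, and it leaves recorded associated injuries out of the named model terms although multiple-trauma patients are enrolled. Under the assumed 20% to 50% prevalence and 0.3 to 0.8 SD deficit, one injury indicator would cut the standard error by about 1% to 7%. The primary outcome, the 808 and the validity of the unadjusted comparison are unaffected. The size rests on those assumptions and on a single-visit simplification of the longitudinal model. The baseline status of the injury items rests on form numbering. The undefined adjusted column needs resolving however small the gain in precision.

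**What to change.** Before unblinding, state in protocol Table 4 and SAP 9.1 and 9.2 that the SF-12 and HOS models include, besides treatment and time:

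- the three stratification factors (displacement, ipsilateral shaft fracture, region), as entered at randomisation;
- the recalled pre-injury score for the same instrument;
- an indicator for any additional fracture (3.4 Q20) and one for any additional injury (3.4 Q24);
- an indicator for contralateral femoral neck fracture, if the CRF is confirmed to capture it.

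State that the *Adjusted Mean Difference* in Tables 13 to 18 comes from this model, and give the model without added covariates as a sensitivity analysis. That sensitivity analysis also covers one weakness: the pre-injury score is recalled after surgery by participants who are not blinded to the implant. Once that score is a covariate, the post-op row in these tables should be descriptive only.

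The cost is a few lines of specification and one check of the CRF, with no new participants, visits or procedures. The statistical cost is six or seven degrees of freedom. That is negligible at 808 and matters only if the final number is near the 86 printed in SAP Table 2.
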